6.8. Appendix 8 medications or therapies that could improve EP/GPP

1. Medications of topical corticosteroids (strong) and topical non-corticosteroid antipsoriatic therapies. For topical corticosteroids (strong) will be identified by medical review.
2. The medications of conventional systemic immunosuppressive therapy, biologic therapy, and non-biologic immunomodulators excluding methotrexate, retinoid, and cyclosporine.
3. The medications of corticosteroids and whose administration routes are oral, intramuscular, intravenous, parenteral, subcutaneous, or nasogastric.
4. Medications including corticosteroids whose administration routes are intralesional or transdermal.
5. The therapies categorized as concomitant phototherapy. in CRF

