#### 6.9.1.1. GPP/EP Concomitant Medications

##### Topical Therapy

Shampoos (containing salicylic acid only) and bland emollients are allowed on all body regions but should not be used within 24 hours before any study visit. Non-medicated shampoos may be used on the day of the study visit.

Other topical therapies that could affect psoriasis evaluations including but not limited to (eg, topical corticosteroids\*, topical calcineurin inhibitors, tar, anthralin, calcipotriene, tazarotene, methoxsalen, trimethylpsoralens, fumarate, PDE4 inhibitors, topical JAK inhibitors, aryl hydrocarbon receptor-modulating agents; shampoos that contain corticosteroids, coal, tar or vitamin D3 analogs; and herbal treatments and traditional Taiwanese, Korean, or Chinese medicines) are not permitted from Week 0 through Week 52.

\*Exception: weak or medium ranked topical corticosteroid on face, palms, soles, and intertriginous areas with stable use is allowed with restriction use within 24 hours prior to study visits.

After Week 52, topical therapies are permitted for treatment of GPP or EP.

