4.2.2.2. Supplementary Estimand

The supplemental estimand has the same attributes as in primary estimand, except for the Intercurrent events and their corresponding strategies:

Intercurrent Event	Strategy	Description
1. Discontinuation of study intervention for any reason on or prior to Week 16.	Composite	Participants with these intercurrent event are considered as nonresponders. The occurrence of these intercurrent events is captured in the variable definition.
2. Initiation of other medication or therapy that could improve GPP/EP on or prior to Week 16 excluding medication or therapy that allowed in the protocol.		
3. Discontinuation of study intervention for reasons other than ICE 1	Treatment Policy	Observed data will be used regardless of whether or not this intercurrent event had occurred.

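### SAP Appendix 8 identifies topical corticosteroids for ICE 2 by rank alone, while the protocol exception also depends on body site and stable use, so some prohibited use may go uncounted in the supplementary analysis

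*SAP*

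**What the plan says.** Protocol 6.9.1.1 (Topical Therapy) names topical corticosteroids among the topical agents that could affect psoriasis evaluations and says that these "are not permitted from Week 0 through Week 52". It makes one exception: "weak or medium ranked topical corticosteroid on face, palms, soles, and intertriginous areas with stable use is allowed", with a restriction on use in the 24 hours before a visit. Exclusion criterion 19 uses the same ranks and sites.

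SAP 4.2.2.2 defines ICE 2 of the supplementary estimand as "Initiation of other medication or therapy that could improve GPP/EP on or prior to Week 16 excluding medication or therapy that allowed in the protocol". The strategy is composite: "Participants with these intercurrent event are considered as nonresponders".

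The SAP version history records that Appendix 8 was added in connection with the clarification of ICE 2. Item 1 of that appendix reads "Medications of topical corticosteroids (strong) and topical non-corticosteroid antipsoriatic therapies", followed by "For topical corticosteroids (strong) will be identified by medical review". Item 4 reads "Medications including corticosteroids whose administration routes are intralesional or transdermal".

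The primary estimand (SAP 4.2.2.1) has a single intercurrent event, discontinuation of study intervention, handled by treatment policy.

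**The concern.** The exception in the protocol has three conditions: rank, body site and stable use. Appendix 8 item 1 keeps only rank. A medium-rank corticosteroid newly started on the trunk or limbs is outside what the protocol allows, yet it is not on the list that a programmer would use to flag ICE 2. The text of ICE 2 exempts only protocol-allowed therapy, so it can be read as including that use. The SAP then points to two different answers for the same participant.

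The supplementary estimand is the only planned efficacy analysis that withdraws responder status for other GPP/EP therapy. Success requires only a rating of at least Minimally Improved, the study is open-label, and each group has a target of 8, so the classification of one participant is visible in the result. If the rule is left open, it would have to be settled during data review.

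**Working it through.** The documents state no figure on this point, and the sample size rests on feasibility, so there is nothing to reproduce. The check is a comparison of texts, followed by a calculation of scale.

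**Step 1: apply both rules to the same use, started by Week 16.**

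| Topical corticosteroid use | Protocol 6.9.1.1 | Appendix 8 item 1 | Agree? |
|---|---|---|---|
| Strong, any site | Not allowed | Counted | Yes |
| Weak or medium, the four named sites, stable | Allowed | Not counted | Yes |
| Weak or medium, newly started on trunk or limbs | Not allowed | Not counted | No |
| Weak or medium, newly started on a named site | Depends on the meaning of stable use, which is not defined | Not counted | Unclear |

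**Step 2: look for another Appendix 8 item that catches the third row.** Item 2 covers systemic immunosuppressive, biologic and non-biologic immunomodulating drugs. Item 3 covers corticosteroids by oral, injected, parenteral or nasogastric routes. Item 5 covers phototherapy. None of these reaches a skin-applied corticosteroid. Item 4 names the transdermal route and could reach it if the CRF codes skin application that way. The documents do not say whether it does, and item 1 handles topical corticosteroids separately.

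**Step 3: conditions for a wrong classification.** All of these must hold: the participant starts a weak or medium topical corticosteroid outside the named sites by Week 16; study intervention is not discontinued by then (ICE 1); no other ICE 2 therapy is started; the Week 16 CGI is at least Minimally Improved; and item 4 does not apply.

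**Step 4: direction and scale.** The gap only leaves out nonresponder events, so it can raise the supplementary rate but not lower it. With n = 8 per disease group (SAP 5), one participant is 1/8 = 12.5 percentage points. The interval is the Clopper-Pearson one named in SAP 4.2.3.1, with lower limit Beta(0.025; x, n−x+1) and upper limit Beta(0.975; x+1, n−x). At x = n the lower limit is 0.025^(1/8) = 0.631 and the upper limit is 1. The responder counts below are illustrative.

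| Counted as responders | Rate | 95% CI |
|---|---|---|
| 8/8 | 100% | 63.1 to 100 |
| 7/8 | 87.5% | 47.3 to 99.7 |
| 6/8 | 75.0% | 34.9 to 96.8 |

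From 8/8, reclassifying one participant moves the lower limit from 63.1% to 47.3%, a drop of 15.8 points.

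**The case against.** The best defence is that ICE 2 has two conditions: the therapy could improve GPP/EP, and the protocol does not allow it. Appendix 8 may define only the first, so that listing only strong corticosteroids is a judgement that lower ranks do not alter response enough to count. That reading is possible, but the SAP gives no rationale for it, and it sits badly with the protocol, which groups topical corticosteroids with agents that could affect psoriasis evaluations and exempts the lower ranks only under conditions.

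There are also safeguards. SAP 6.5 lists participants who received concomitant corticosteroids and all concomitant medication, so with about 16 participants the use would be visible. SAP 6.3 has major protocol deviations identified before database lock, then summarized and listed. Protocol 7.1.3 makes prohibited therapy that affects efficacy evaluation a ground for permanent discontinuation, which by Week 16 would be ICE 1. These points stand, but none closes the gap: listings and deviation summaries do not change responder status, and the discontinuation rule is at the medical monitor's discretion.

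A reader might infer that the supplementary rate is biased upward and that the analysis fails as a check. The documents do not support that. Nothing shows that such use will occur, and every condition in step 3 has to be met. The estimand still captures discontinuation, strong topical corticosteroids, topical non-corticosteroid antipsoriatics, the listed systemic and biologic drugs, systemic corticosteroids and phototherapy. A reader might also point to the EP entry criterion of at least 80% BSA as evidence of large exposure outside the exempt sites. That criterion does not apply to GPP, and the documents give no figure for the share of skin that the exempt sites represent.

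**Conclusion.** Appendix 8 item 1 does not match ICE 2 read with protocol 6.9.1.1. Following the list can leave a participant a responder in the supplementary analysis despite newly started topical corticosteroid use that the protocol does not allow. The effect is conditional and one-directional: 12.5 points per affected participant at n=8. The documents give no basis for estimating how many participants would be affected, and the number may be zero. The calculation assumes 8 participants in the group and illustrative responder counts.

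The consequence is confined to a descriptive supplementary analysis. The primary analysis uses observed data without reference to Appendix 8, and no formal hypothesis test is planned. The mismatch is still worth removing, because the correction is small and the alternative is to decide the classification with open-label data in view.

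**What to change.** Reconcile Appendix 8 item 1 with ICE 2 and protocol 6.9.1.1. This changes only the analysis rule and leaves permitted treatment as it is.

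- Reword the corticosteroid part of item 1 so that it counts any topical corticosteroid started on or before Week 16 that falls outside the exception in protocol 6.9.1.1, whatever its rank. Keep the part on topical non-corticosteroid antipsoriatic therapies.
- State how the transdermal route in item 4 relates to item 1, so that the result does not depend on route coding.
- Extend the medical review already planned for rank to application site and start date, and complete it before database lock.
- Use the same rule for the SAP 6.5 listing of therapy that could improve GPP/EP.

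The cost is a short SAP revision and some added review in a study of about 16 participants. Application site may need a data query, since the documents do not show that it is collected. The review must also apply the protocol's undefined stable-use condition consistently, above all for a weak or medium product newly started on a named site; a written convention agreed before the review would serve. The supplementary rate may come out slightly lower.

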### Concomitant Therapy

4. a. In case of receiving methotrexate (MTX) or cyclosporine, the participant must be on stable dose from 2 weeks before the first administration of study intervention with doses of MTX  $<20$  mg/week OR cyclosporine  $\leq 5$  mg/kg/day.

Note: Participants must not be on both MTX and cyclosporine at the same time from 2 weeks before the first administration of study intervention.

4. b. In case of receiving retinoid, the participant must be on stable dose from 2 weeks before the first administration of study intervention.

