### **Phototherapy or Systemic Therapy**

The use of phototherapy or systemic medications (other than MTX, retinoid, and cyclosporine) that could affect psoriasis or the efficacy evaluation, is not permitted at any time during the study (until ET Visit for participants who terminate early or until last study intervention administration visit).

These medications include, but are not limited to,

- those targeted for reducing TNF $\alpha$  (including but not limited to infliximab, etanercept, or adalimumab).
- drugs targeted for reducing IL-12/23, IL-17, IL-23, IL-36 (including but not limited to ustekinumab, guselkumab, tildrakizumab, secukinumab, risankizumab, ixekizumab, brodalumab, or spesolimab).
- alpha-4 integrin antagonists (including but not limited to natalizumab).
- JAK inhibitors (including but not limited to tyrosine kinase 2 inhibitors).
- PDE4 inhibitors (including but not limited to apremilast).
- oral and injectable (IV, intramuscular, or intralesional) corticosteroids.
- any other conventional systemic therapies that could affect psoriasis or the efficacy evaluation.
- antimarial agents.
- herbal treatments.
- traditional Taiwanese, Korean, or Chinese medicines.

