### **MTX, Retinoids, or Cyclosporine for Treatment of Psoriasis**

In case of receiving retinoids, 2 weeks with stable dose before the first administration of study intervention is necessary, and any change in the dose should be avoided through Week 52. Dose can be reduced; however, it cannot be re-escalated once it is reduced. After Week 52, there is no limitation on retinoid.

In case of receiving MTX (<20 mg/week) or cyclosporine ( $\leq$ 5 mg/kg/day) at screening, at least 2 weeks with stable dose before the first administration of study intervention is necessary and this stable dose should continue through Week 16. In case of participants with confirmed clinical improvement, dose reduction is allowed before Week 16, but dose cannot be re-escalated. After Week 16, cyclosporine should be tapered off and discontinued by Week 32. If the condition of a participant worsens after tapering cyclosporine, the investigators should consider discontinuation of study drug and pursue alternative treatment options. After Week 16, MTX should be tapered off and an attempt should be made to discontinue MTX by Week 32. Minimal dose of MTX should

be maintained throughout the study if the participant is not able to discontinue MTX completely. Participants are not permitted to receive both MTX and cyclosporine at the same time during the study.

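### Supplementary estimand: the intercurrent event for other therapy misses dose increases of methotrexate, retinoid or cyclosporine by Week 16, and its appendix exempts combined methotrexate and cyclosporine that the protocol bars

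*SAP*

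**What the plan says.** **SAP Section 4.2.2.2.** Intercurrent event (ICE) 2 is "Initiation of other medication or therapy that could improve GPP/EP on or prior to Week 16", with the qualifier "excluding medication or therapy that allowed in the protocol". It has a composite strategy, so the participant becomes a non-responder. ICE 1, discontinuation of study drug by Week 16, is handled the same way.

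**SAP Section 6.8 (Appendix 8), item 2.** Among the therapies that could improve EP or GPP, the item lists conventional systemic immunosuppressants, "biologic therapy, and non-biologic immunomodulators excluding methotrexate, retinoid, and cyclosporine". It sets no condition on dose, timing or prior use. The SAP version history says Appendix 8 was added with the ICE 2 update, but ICE 2 itself does not cite it.

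**Protocol Section 6.9.1.1.** The general ban on systemic therapy excepts the three drugs: use of "systemic medications (other than MTX, retinoid, and cyclosporine) that could affect psoriasis or the efficacy evaluation, is not permitted". The section then sets conditions on their use:

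- For methotrexate (MTX) or cyclosporine, "this stable dose should continue through Week 16". On confirmed improvement, "dose reduction is allowed before Week 16, but dose cannot be re-escalated".
- For retinoids, a dose change is to be avoided through Week 52. "Dose can be reduced; however, it cannot be re-escalated once it is reduced".
- MTX and cyclosporine may not be taken together during the study.

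**Protocol Section 5.1, criterion 4.** The entry conditions are also written for drugs already in use. For MTX or cyclosporine, "the participant must be on stable dose from 2 weeks before the first administration of study intervention with doses of MTX" or cyclosporine within stated limits.

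**The concern.** The supplementary estimand is the only planned responder analysis that deals with other therapy. The primary estimand names discontinuation of study drug as its one intercurrent event, under treatment policy. The supplementary analysis should therefore show how many successes remain once those possibly helped by other treatment are set aside.

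ICE 2 exempts what the protocol allows. Appendix 8 exempts three drugs whatever the protocol's conditions on them. A participant whose background systemic drug was raised by Week 16, against those conditions, can then stand as a success in the one analysis meant to exclude that kind of help. Success requires only a Minimally Improved rating, in an open-label single-arm study, so a stronger background drug could plausibly contribute to it.

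**Working it through.** **Step 1. Apply the texts to each kind of event.** In every row the event occurs on or before Week 16 and the participant stays on study drug.

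| Event | Protocol 6.9.1.1 | ICE 2 wording alone | Appendix 8 item 2 | Result |
|---|---|---|---|---|
| Ongoing MTX or cyclosporine increased | Departs from the stable dose, which should continue through Week 16 | Not an initiation | Exempt | Not ICE 2 |
| Any of the three re-escalated after a reduction | Barred | Not an initiation | Exempt | Not ICE 2 |
| First increase of an ongoing retinoid | To be avoided, not firmly barred | Not an initiation | Exempt | Not ICE 2; unclear whether it departs from the protocol |
| MTX added to cyclosporine, or the reverse | Barred | Initiation, not allowed: ICE 2 | Exempt by name: not ICE 2 | The two SAP texts conflict |
| One of the three newly started alone | Excepted by name from the ban; conditions written only for ongoing use | Initiation; whether allowed is not spelled out | Exempt | Leans to not ICE 2; minor ambiguity |

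The first three rows escape on the trigger word and again on the exemption. In the fourth row the SAP does not say which text governs.

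**Step 2. Check whether another provision closes the gap.**

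- Protocol Section 7.1.3 can lead to stopping study drug, and so to ICE 1. It speaks of a participant who initiates prohibited treatment and leaves the matter to the medical monitor's discretion. It does not clearly reach a dose increase and is not automatic for combined use.
- SAP Appendix 3 summarises and lists major protocol deviations, and Appendix 5 summarises and lists concomitant medication. These outputs may reveal a case but do not change responder status.

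**Step 3. Size one reclassification.** The plan gives no figure to reproduce: the target of 8 + 8 = 16 rests on feasibility, with no power calculation. SAP Section 4.2.3.2 reuses the main method, a proportion with a 95% Clopper-Pearson interval in each disease group. The responder counts below are assumed.

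- Change in proportion: 1/8 = 12.5 points.
- Limits for x of n: lower = Beta quantile at 0.025 with parameters (x, n − x + 1); upper = Beta quantile at 0.975 with parameters (x + 1, n − x). For x = n the lower limit reduces to 0.025^(1/n) and the upper is 1.
- 8/8: lower 0.025^(1/8) = 63.06%, upper 100%.
- 7/8: lower from Beta(7, 2) = 47.35%, upper from Beta(8, 1) = 99.68%.
- Fall in the lower limit: 63.06 − 47.35 = 15.7 points.

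| Responders | Proportion | 95% limits |
|---|---|---|
| 8/8 | 100% | 63.1 to 100 |
| 7/8 | 87.5% | 47.3 to 99.7 |
| 6/8 | 75.0% | 34.9 to 96.8 |
| 5/8 | 62.5% | 24.5 to 91.5 |

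**The case against.** An event defined by the start of other therapy, with permitted background drugs exempt, is a coherent estimand, and version 2 of the SAP revised it deliberately. Departures from a background dose can be treated as protocol deviations, and no text promises to count them as failures. With about 16 participants every case can be inspected individually, and anyone taken off study drug by Week 16 is already a non-responder. The 12.5 points would apply to any reclassification in a group of 8, so they describe the sample size more than this defect.

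Much of this stands, and it limits the weight of the point. It does not remove it. ICE 2 ties its exemption to what the protocol allows, and Appendix 8 does not keep to that. Listings do not alter the count.

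Two stronger readings are tempting, and the documents do not support them.

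- A reader might infer that the protocol is silent on all new starts, or that every new start is misclassified. In fact Section 6.9.1.1 rules out one kind, MTX together with cyclosporine. For a single drug started alone, the protocol's ban and Appendix 8 agree in excepting it by name; the contrary reading rests only on conditions written for ongoing use.
- A reader might infer that every dose increase is equally barred. Re-escalation is firmly excluded. A first retinoid increase is only to be avoided, and MTX or cyclosporine stability is worded as something that should continue.

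**Conclusion.** The point holds and is minor. As written, a dose increase or re-escalation of ongoing MTX, retinoid or cyclosporine by Week 16 is not ICE 2, even where it departs from Protocol Section 6.9.1.1. A participant in that position who stays on study drug and is rated at least Minimally Improved counts as a responder. For combined MTX and cyclosporine the same can happen if Appendix 8 governs. The single-drug new start is a lesser ambiguity.

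One such case would move a group of 8 by 12.5 points. This assumes that the planned group size is reached and that a case occurs in a participant otherwise rated a success. The documents give no rate of dose increases or combined use, so no probability of a changed result can be stated. It would be wrong to infer that the primary result is affected: the primary estimand has no intercurrent event for other therapy, and SAP Section 2 plans no hypothesis test.

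**What to change.** Change analysis classification only, in the SAP, before database lock. The clinical rules stay as they are.

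1. Limit the exemption in Appendix 8 item 2 to use of the three drugs within the conditions of Protocol Section 6.9.1.1.
2. Extend ICE 2 to cover, on or before Week 16 and outside those conditions, a dose increase or re-escalation of any of the three drugs, and the addition of MTX to cyclosporine or the reverse.
3. State whether a first retinoid increase counts, since the protocol's wording leaves this open.
4. State one classification for a single-drug new start. The sponsor must choose and record it.
5. Cite Appendix 8 within ICE 2.

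**Cost.** The supplementary success rate may be slightly lower. The change needs dose-change dates for these drugs, and the documents do not confirm that the CRF holds them. Protocol Section 6.9 requires therapies to be recorded; Section 6.9.1.2 asks for changes to be recorded only when a medication for another indication is temporarily stopped. If the dates are missing, cases can be identified by medical review before lock, as Appendix 8 item 1 already does for strong topical corticosteroids. With about 16 participants that is a small effort.
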